9. RESEARCH METHODS

9.1 STUDY DESIGN

This is a non-interventional study using existing data including medical chart review. The study will include all patients fulfilling the inclusion and not fulfilling the exclusion criteria in the period of 4 months (September – December 2018) (= index date 1).

| Parameter | Assessed at study index date 1 |
|--|---------------------------------------|
| Written Informed Consent* | X |
| Inclusion / Exclusion Criteria | X |
| Patient demographics (age, gender, height, weight, BMI, ethnicity) | X |
| Time since diagnosis of Type 2 Diabetes | X |
| Clinical parameters relevant for T2D, CVD, CKD assessment | X |
| Comorbidities like cardiovascular diseases and related risk factors | X |
| Comorbidities like chronic kidney disease and related risk factors | X |
| T2D medication the treating physician newly prescribes at study index date | X |
| Concomitant T2D medications at study index date | X |
| Concomitant CVD and CKD medications at index date | X |
| Other HCPs involved in treatment decisions at study index date | X |
| Relevant socioeconomic parameters | X |

[figure not shown]
* Patients who were enrolled before amendment 1 and who have consented to data collection at index date 1 have to consent to data collection at index date 2 separately. Newly enrolled patients have to give their consent for data collection at index date 1 and 2 before data transfer into eCRF.

Approximately 1 year (\pm 2 months) after index date 1, parameters regarding status of newly initiated T2D treatment will be collected.

| Parameter | Assessed at study index date 2 |
|---|---------------------------------------|
| Continuation / Discontinuation of T2D therapy initiated at index date 1 | X |
| In case of discontinuation: stop date | X |
| In case of discontinuation: reason for discontinuation | X |
| In case of discontinuation: other HCPs involved in treatment decision | X |

An overview of study design is given in Figure 1.

Figure 1: Overview of study design

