9.3 VARIABLES

The following parameters will be collected and assessed at study index date 1:

1. Patient demographics (age, gender, height, weight, BMI, ethnicity)
2. Time since diagnosis of Type 2 Diabetes
3. Clinical parameters relevant for T2D, CVD, CKD assessment (see below) as valid on study index date 1
4. Comorbidities like cardiovascular disease and related risk factors (see below) and Comorbidities like chronic kidney disease and related risk factors (see below) at study index date 1
5. T2D medication the treating physician newly prescribes at study index date 1
6. Concomitant T2D medications at study index date 1
7. Concomitant CVD and CKD medications at index date 1
8. Involvement of other HCPs in treatment decisions at study index date 1
9. Relevant socioeconomic parameters (see below) at index date 1

The following parameters will be collected and assessed at study index date 2 (= approximately one year ± 2 months after index date 1):

1. Status of T2D medication (continuation / discontinuation)
2. If discontinuation:
 - a. stop date of initial(index date 1) T2D medication (if available)
 - b. Reason for therapy discontinuation (see below)
 - c. Involvement of other HCPs in decision for therapy discontinuation

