 - sitagliptin
 - saxagliptin
 - vildagliptin
- GLP1a
 - dulaglutide
 - exenatide
 - liraglutide
 - semaglutide
 - lixisenatide
- Reasons for choosing the treatment rated as not relevant at all/ moderately relevant/ highly relevant
 - HbA1c lowering
 - Weight loss

- Cardiovascular risk reduction
- Favorable side effect profile
- Simple dosing / administration
- Guideline recommendation

[figure not shown]
6. Concomitant T2D medications (given as monotherapy or as fix combination with main T2D medication) at study index date 1
 - Metformin
 - Sulfonylurea
 - Acarbose
 - Pioglitazone
 - Insulin
 - others
7. Concomitant CVD and CKD medications at index date 1 (on class level only)
 - Antihypertensives ACEi or ARBs
 - Statins
 - Low dose aspirin
 - Beta blockers
 - Diuretics
8. Involvement of other HCPs in treatment decisions with regard to SGLT2i, DPP4i or GLP1a prescription at study index date 1 and with regard to discontinuation at index date 2 (yes/no; if yes, the medical specialty of the involved physician(s) should be specified)
9. Association of socioeconomic parameters with treatment decisions (such as employment status, family status, type of health insurance) at study index date 1
10. Status of T2D therapy approximately one year (\pm 2 months) after start
 - Stop date, if available
 - Reasons for discontinuation
 - Investigator's decision
 - Patient's request (difficulties in medication handling)
 - Patient's request (financial burden regarding co-payment)
 - Patient's request (other)
 - Lost to follow-up
 - Adverse event (in case of adverse reaction to empagliflozin or linagliptin or fatal adverse event, see [Section 11](#))
 - Death
 - Unknown
 - Other

Primary outcomes

- T2D patients' baseline characteristics when initiating either empagliflozin - or other SGLT2i, DPP4i or GLP1a on top of current antidiabetic treatment by different HCP specialties in CEE countries.

Secondary outcomes

- Burden of comorbidities (prevalence of CVD, CKD and CVD/CKD risk factors) in this T2D patient population at study index date 1
- Actual treatment use at study index date 1 in patients with and without established CVD (Established CV disease defined as acute myocardial infarction (AMI), cardiology intervention, ischemic heart disease (IHD), congestive heart failure (CHF), peripheral arterial disease (PAD), or stroke)
- To describe the association of socioeconomic parameters with treatment decisions at study index date 1

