9.12 BIAS

Selection bias could occur at the site level and the patient level.

To minimize the site level selection bias, sites will be eligible if HCPs initiate second line medications in their T2D patients. In addition to that, the number of proposed sites will be 150% of sites to be finally included which will allow random selection of site.

In order to limit the variability of outcomes, sites will be eligible if they have access and can prescribe at least 2 of the T2D drug classes of interest (SGLT2i, DPP4i, GLP1a) for the targeted T2D.

To minimize selection bias at the patient level, physicians are requested to include all patients meeting inclusion and exclusion criteria in the study period of 4 months (September – December 2018) into the study. However, there may be a bias regarding patient groups at index date 1 and 2, since not all patients who have consented to documentation at index date 1 may or can give their consent (e.g. due to death or loss to follow-up) to further documentation at index date 2.

Information bias will be minimized by the use of standard eCRF and physicians' training on the study protocol and handling of the eCRF.

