| Section 6: Outcome definition and measurement | Yes | No | N/A | Section Number |
|--|-------------------------------------|-------------------------------------|--------------------------|--|
| 6.1 Does the protocol specify the primary and secondary (if applicable) outcome(s) to be investigated? |  |  |  | 9.3.2 |
| 6.2 Does the protocol describe how the outcomes are defined and measured? |  |  |  | 9.3.2 9.7.1 |
| 6.3 Does the protocol address the validity of outcome measurement? (e.g. precision, accuracy, sensitivity, specificity, positive predictive value, use of validation sub-study) |  |  |  | |
| 6.4 Does the protocol describe specific outcomes relevant for Health Technology Assessment? (e.g. HRQoL, QALYs, DALYs, health care services utilisation, burden of disease or treatment, compliance, disease management) |  |  |  | |

Comments:

To question 6.3: The study outcomes will be analyzed in a purely descriptive manner, no sensitivity analyses will be performed.

| Section 7: Bias | Yes | No | N/A | Section Number |
|--|-------------------------------------|--------------------------|--------------------------|-----------------------|
| 7.1 Does the protocol address ways to measure confounding? (e.g. confounding by indication) |  |  |  | 9.12 |
| 7.2 Does the protocol address selection bias? (e.g. healthy user/adherer bias) |  |  |  | 9.12 |
| 7.3 Does the protocol address information bias? (e.g. misclassification of exposure and outcomes, time-related bias) |  |  |  | 9.12 |

Comments:

| |
|--|
| |
|--|

| Section 8: Effect measure modification | Yes | No | N/A | Section Number |
|---|--------------------------|--------------------------|-------------------------------------|-----------------------|

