6.6 HANDLING OF MISSING DATA AND OUTLIERS

No missing data will be imputed. If patients have missing values for an outcome, those patients will be excluded for that outcome's analysis.

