7.4 SECONDARY OUTCOME(S)

All analysis will be descriptive and will be performed on PPS.

[figure not shown]
The prevalence of CVD and CKD will be displayed in frequency tables as well as the reasons for treatment choice, concomitant T2D medication and concomitant CVD/CKD medication. Furthermore other physicians involved in the treatment decision as well as the decision to discontinue the treatment will be given.

The "10 year risk for fatal CVD" will be calculated by applying the SCORE Risk Chart (European Society of Cardiology) taking into account patient's age, gender, systolic blood pressure, smoking status, and total cholesterol value at index date 1.

Moreover, the discontinuation rate and the reason for discontinuation will be displayed in frequency tables.

To assess the duration of T2D therapy after one year (\pm 2 months) the time to discontinuation will be analysed by Kaplan-Meier estimates and subgroups will be compared using log-rank test.

For comparison of subgroups, χ^2 -test or Fisher's exact test, if χ^2 -test is not valid, will be used. If the treatment decision depends on socioeconomic factors will be analysed using χ^2 -test or Fisher's exact test.

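### Loss to follow-up and death are recorded as reasons for stopping the drug, the visible SAP gives no event or censoring rule for them, and selection by late index-date-2 consent goes unexamined

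*SAP*

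**What the plan says.** Objective 5 (protocol 8.2) is the discontinuation rate, the reasons, and the average treatment duration for GLP1a, DPP4i and SGLT2i about one year after initiation.

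- **What is collected.** Protocol 9.3 has one status item, "Status of T2D medication (continuation / discontinuation", and, for patients who discontinued, the "stop date of initial(index date 1) T2D medication (if available". The index-date-2 table in protocol 9.1 asks for the reason only on that branch: "In case of discontinuation: reason for discontinuation". The reasons in protocol 9.3.2, item 10, include "Lost to follow-up", death and unknown. No date of last contact or of death is listed.
- **What is analysed.** SAP 7.4 puts the discontinuation rate and reasons in frequency tables. For duration, "the time to discontinuation will be analysed by Kaplan-Meier estimates and subgroups will be compared using log-rank test". SAP 6.6 adds: "If patients have missing values for an outcome, those patients will be excluded for that outcome's analysis".
- **Who is analysed.** SAP 6.3 defines the FAS as PPS patients with index-date-2 documentation; patients included before the amendment also need a further consent. By the footnote in protocol 9.1, later enrollees consent to both index dates before any data are transferred. SAP Table 6.3:1 and the first paragraph of SAP 7 give index-date-2 outcomes to the FAS. SAP 7.4, the closing text of SAP 7 and protocol 9.7.1 name the PPS or the prescribed patients.
- **What is admitted.** Protocol 9.12 expects possible bias between the two index dates, "since not all patients who have consented to documentation at index date 1 may or can give their consent (e.g. due to death"; it also names loss to follow-up as an example.

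**The concern.** A patient who is lost has an unknown drug status, and a patient who died did not choose to stop. With only two status values, and with both outcomes filed as reasons on the discontinuation branch, the tabulated rate mixes drug stopping with loss and death. The Kaplan-Meier curve may or may not do the same, because no rule is visible. The table and the curve can also disagree, since a missing stop date removes a patient from one and not from the other.

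Selection works alongside this. If the patients who died or were lost seldom reach the index-date-2 data set, the rate describes patients who were still reachable when the amended consent was sought. If loss, death or consent differs by drug class or country, the planned chi-square and log-rank comparisons can show a difference that is not one of drug persistence.

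**Working it through.** The documents give no expected discontinuation, loss or death rate and no share of patients enrolled before the amendment. There is no plan figure to reproduce. Steps 1 and 2 come from the text; steps 3 to 6 are illustrations under assumed rates.

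**1. Route of one patient through the plan.**

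| Recorded at index date 2 | Frequency table | Kaplan-Meier |
|---|---|---|
| Continuing | not a discontinuation | censored, date not stated |
| Stopped, date known | discontinuation | event |
| Stopped, no date | discontinuation | excluded (SAP 6.6) |
| Lost or dead, date entered | discontinuation, read literally | not stated |
| Lost or dead, no date | discontinuation, read literally | excluded (SAP 6.6) |

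**2. Timing of consent.** Last possible index date 1: 31 Dec 2018. Index date 2 is 12 ± 2 months later, so the last window ends 14 months on, at 29 Feb 2020. Amendment 1 is dated 06 May 2020 (protocol 5). Consent under the amendment therefore came after every window had closed. Patients already enrolled had to re-consent to enter the FAS. Patients enrolled afterwards had to be reachable at that time to enter the study at all, so for them the selection is into the PPS itself.

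**3. Effect of the coding.** Assume true stopping of 20% in both classes, the protocol 9.5 aims of 500 GLP1a and 1000 DPP4i, and 80% in the FAS (400 v 800). Add 5 points of loss or death to GLP1a: 80 stops, 20 lost or dead, 300 continuing, against 160 stops and 640 continuing.

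Crude rates: 100/400 = 25% and 160/800 = 20%. Pooled p = 260/1200 = 0.2167. z = 0.05 / √(0.2167 × 0.7833 × (1/400 + 1/800)) = 0.05/0.02523 = 1.98, p = 0.0475. With the 5 points in DPP4i instead, p = 0.0535. With 70% in the FAS the two p-values are 0.064 and 0.071; with 90%, 0.036 and 0.041.

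For Kaplan-Meier, spread the stop and loss dates evenly over 12 months:

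| Handling of the 20 lost or dead | KM at 12 months, GLP1a v DPP4i | Log-rank p |
|---|---|---|
| Events | 25.0% v 20.0% | 0.047 |
| Censored at their date | 20.6% v 20.0% | 0.83 |
| Dropped, no date | 80/380 = 21.1% v 20.0% | 0.68 |

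The frequency table reads 25% in all three cases. Because step 2 suggests few recorded losses, take 1 point instead: 84/400 = 21% v 20%, pooled p = 244/1200 = 0.2033, z = 0.01 / √(0.2033 × 0.7967 × 0.00375) = 0.41, p = 0.68. The effect is then negligible.

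**4. Stops without a date.** If a share m of true stops lacks a date and is excluded, a 20% rate becomes 0.20(1 − m)/(1 − 0.20m). For m = 10%, 20% and 30% this is 0.18/0.98 = 18.4%, 0.16/0.96 = 16.7% and 0.14/0.94 = 14.9%.

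**5. Selection from PPS to FAS.** With an FAS share f and an FAS rate of 20%, the PPS rate lies between 0.20f (all undocumented patients continuing) and 0.20f + (1 − f) (all stopped): 18–28% at f = 90%, 16–36% at 80%, 14–44% at 70%. The sampling 95% half-width at f = 80% is 1.96 × √(0.16/3200) = 1.4 points. These bounds say nothing about selection into the PPS.

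**6. PPS or FAS wording.** Under SAP 6.6, PPS patients without index-date-2 data are excluded from these outcomes. At 20% in the FAS, the rate is 20% under either label.

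**The case against.** The strongest counter-argument is that the selection undercuts the coding problem. If index-date-2 data require consent given after the window, the analysed patients were mostly alive and reachable then, and few will carry a loss or death code. This stands. Exceptions are consent by a legal representative (protocol 9.10.2), patients who left and returned, and records made outside the window. It means that the 5-point illustration has no support in the documents, and that selection may matter more than coding.

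Second, the list in protocol 9.3.2 is a data-collection list. A reader might infer that the SAP makes loss and death Kaplan-Meier events. It does not say so, and because reasons are coded separately an analyst could censor on them. What stands is that no rule is visible.

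Third, a reader might take the line in Annex 2 that "no sensitivity analyses will be performed" as ruling out any check of selection. It comments on question 6.3, the validity of outcome measurement, and is weak evidence here. The text under SAP 6.4 and 7.5 is not shown, so absence is established only for the visible text.

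Fourth, the analyses are labelled explorative, and the reasons table will let a reader recompute the crude rate without loss and death. Both are true. Neither repairs the curve or the log-rank test, and an exploratory label does not define the estimate.

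**Conclusion.** The point holds in a limited form. Read literally, the SAP 7.4 discontinuation rate includes loss and death; their status in Kaplan-Meier is unstated; and a missing stop date makes the table and the curve use different patients. Consent given after every window had closed leaves patients who died or were lost largely out of the data. Protocol 9.12 concedes this, and no analysis of it is visible.

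Size and direction of the net bias cannot be derived. Counting loss and death raises the rate, dropping undated stops lowers the Kaplan-Meier estimate, and missing patients may move it either way. The illustrated shift runs from 1 point (p = 0.68) to 5 points (p about 0.05) with the assumed loss.

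Two stronger readings are not supported. The additional consent is a selection mechanism, and nothing in the documents makes it a consent violation. The PPS/FAS conflict in the SAP text is real but editorial, since SAP 6.6 leads to the same rate under both names. The point should be fixed before analysis; confidence is medium, because the numbers of recorded losses and deaths are unknown.

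**What to change.** 1. Report loss to follow-up and death as categories separate from drug stopping. Give the discontinuation rate with and without them, overall and by class.
2. State the rule for Kaplan-Meier and log-rank in SAP 7.4: loss is censored at the last available date, death is shown separately, and patients with no usable date are counted and listed.
3. Report the numbers passing from PPS to FAS. Compare index-date-1 characteristics of FAS patients and of PPS patients outside the FAS, by class, country, and enrolment before or after Amendment 1. Label the rate as conditional on index-date-2 documentation and consent, and note that neither this comparison nor a bound can detect selection into the PPS.
4. As editorial alignment only, name the FAS for index-date-2 outcomes in SAP 7.4 and in the closing text of SAP 7.

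The cost is SAP wording and a few tables; items 1, 3 and 4 use data already planned. Item 2 will be incomplete, because no last-contact or death date is among the listed variables and some patients will have no usable date. The reported rate will look less precise.

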4. ABSTRACT

| | | | |
|---|--|---|--|
| Name of company: Boehringer Ingelheim | | | |
| Name of finished medicinal product: Jardiance® Synjardy® Trajenta® Jentadueto® | | | |
| Name of active ingredient: empagliflozin linagliptin | | | |
| Protocol date: 12 Dec 2018 | Study number: 1245.187 | Version/Revision: Version 2.0/ Revision 1.0 | Version/Revision date: 11 May 2020 |
| Title of study: | CORDIALLY® - CEE: Characteristics of patients with Type 2 Diabetes treated with modern antidiabetic drugs. A real-world data collection of patient baseline characteristics, treatment patterns and comorbidities in Central Eastern European (CEE) countries | | |
| Rationale and background: | Cardiovascular Disease (CVD) is the most common cause of mortality in T2D patients. Also, chronic kidney disease (CKD) is associated with increased all-cause mortality, which is substantially higher in patients with a diagnosis of diabetes. Registry outcomes imply that patient characteristics might differ between patients initiating empagliflozin or other glucose lowering drugs. | | |
| Research question and objectives: | 
The objective of CORDIALLY® - CEE is to get insights into T2D patient characteristics when initiating different types of T2D treatments, including associated comorbidities (CVD, CKD), concomitant medications and the association of socioeconomic factors with treatment decisions.
 
1. To describe and compare T2D patients' baseline characteristics when initiating either empagliflozin- or other SGLT2i, DPP4i or GLP1a by different HCP specialties in CEE countries2. To describe the prevalence of comorbidities (prevalence of CVD, CKD) at index date 1 in this T2D patient population3. To describe the actual treatment used at index date 1 in patients with and without established CVD. 
Established CV disease defined as acute myocardial infarction (AMI), cardiology intervention, ischemic heart disease (IHD), congestive heart failure (CHF), peripheral arterial disease (PAD), or stroke.
 
4. To describe the association of socioeconomic parameters with treatment decisions at index date 15. To assess the discontinuation rate, reasons for discontinuation and average duration of treatment for GLP1a, DPP4i and SGLT2i after a follow up of approximately one year from the initial time point (= index date 2) | | |

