- To assess the discontinuation rate, reasons for discontinuation and average duration of treatment for GLP1a, DPP4i and SGLT2i after a follow up of approximately one year from the initial time point (= index date 2)

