9.3.3 Covariates

Not applicable

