| 9.3.2 Outcomes? (e.g. International Classification of Diseases (ICD), Medical Dictionary for Regulatory Activities (MedDRA)) |  |  |  | |
| 9.3.3 Covariates and other characteristics? |  |  |  | |
| 9.4 Is a linkage method between data sources described? (e.g. based on a unique identifier or other) |  |  |  | |

Comments:

To question 9.2.2, no safety outcomes will be analyzed as research question. Adverse events reported in this study are solely listed in the CSR, no analysis will be made in this regard.

| Section 10: Analysis plan | Yes | No | N/A | Section Number |
|--|-------------------------------------|-------------------------------------|-------------------------------------|-----------------------|
| 10.1 Are the statistical methods and the reason for their choice described? |  |  |  | 9.7.1 |
| 10.2 Is study size and/or statistical precision estimated? |  |  |  | |
| 10.3 Are descriptive analyses included? |  |  |  | |
| 10.4 Are stratified analyses included? |  |  |  | 9.7.1 |
| 10.5 Does the plan describe methods for analytic control of confounding? |  |  |  | |
| 10.6 Does the plan describe methods for analytic control of outcome misclassification? |  |  |  | |

| Section 10: Analysis plan | Yes | No | N/A | Section Number |
|--|-------------------------------------|--------------------------|-------------------------------------|-----------------------|
| 10.7 Does the plan describe methods for handling missing data? |  |  |  | 9.7.1 |
| 10.8 Are relevant sensitivity analyses described? |  |  |  | |

Comments:

| |
|--|
| |
|--|

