7. PLANNED ANALYSES

All patients who have received a first prescription of respective study medication will be included in the analysis; this is the prescribed patient set. All analyses at index date 1 will be performed on the prescribed patient set and analyses at index date 2 will be performed on the full analysis set. If patients have missing values for an outcome, those patients will be excluded for that outcome's analysis.

The assessment will be carried out using SAS® software. The statistical characteristics presented in the end-of-text tables will be N / mean / SD / min / median / max for continuous variables. Tabulations of relative and absolute frequencies will be presented for categorical variables. Incidence rates and 95% CI will be given when appropriate. Subgroup analyses e.g. according to medication (i.e. empagliflozin or SGTL2i or DPP4i or GLP-1 RA), country and physician specialty are planned, as well as per history of CV disease. Descriptive analyses will be supplemented using χ^2 -test or Fisher's exact test for categorical variables and Wilcoxon-Mann-Whitney test for continuous variables. The analyses are purely explorative, hence no correction for multiple testing is needed.

The analyses will relate to the following data as recorded in the eCRF:

1. Patient demographics (age, gender, height, weight, BMI, ethnicity)
2. Time since diagnosis of Type 2 Diabetes
3. Clinical parameters relevant for T2D, CVD, CKD assessment as valid on index date 1
4. Presence of cardiovascular disease and related risk factors at index date 1
5. Presence of chronic kidney disease and related risk factors at index date 1
6. T2D medication the treating physician newly prescribes at study index date 1
7. Reason(s) for treatment decision at index date 1
8. Concomitant T2D medications at study index date 1
9. Concomitant CVD and CKD medications at index date 1
10. Other HCPs involved in treatment decisions at study index date 1 and at index date 2
11. Relevant socioeconomic parameters
12. Discontinuation rate, reason for discontinuation, duration of T2D therapy after one year (± 2 months)

All adverse events and adverse drug reactions collected per study protocol will be included and summarized in the final study report.

For the main analysis data from research question 1 to 5 will be evaluated in a descriptive manner for the total number of prescribed patients enrolled in the study.

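### The visible plan compares time to discontinuation between drug classes only by an unadjusted log-rank test, whose p-value cannot separate drug class from patient mix

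*SAP*

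**What the plan says.** SAP 7.4 states the method for duration of therapy: "the time to discontinuation will be analysed by Kaplan-Meier estimates and subgroups will be compared using log-rank test". SAP 7 shows which subgroups are meant: "Subgroup analyses e.g. according to medication (i.e. empagliflozin or SGTL2i or DPP4i or GLP-1 RA), country and physician specialty are planned", with history of CV disease added. The outcome is framed by class, as the "average duration of treatment for GLP1a, DPP4i and SGLT2i after a follow up of approximately one year from the initial time point" (protocol 9.3.2; SAP 5.2 is equivalent). SAP 7.4 also plans chi-square or Fisher tests between subgroups, again without adjustment.

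On patient mix, the protocol abstract says: "Registry outcomes imply that patient characteristics might differ between patients initiating empagliflozin or other glucose lowering drugs". Section 9.9 describes the study as covering comorbidities, co-medications and socioeconomic factors that may influence both the treatment decision and how long treatment lasts. Section 9.3.2 records the reasons for choosing a drug, including glucose lowering, weight and cardiovascular risk, and lists co-payment burden among the reasons for stopping.

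On confounding, the whole of protocol 9.3.3 Covariates is "Not applicable". In the Annex 2 checklist, the item "10.5 Does the plan describe methods for analytic control of confounding" is ticked No, and so is item 12.1.3 on residual confounding. The item "7.1 Does the protocol address ways to measure confounding? (e.g. confounding by indication" is ticked Yes with a reference to section 9.12, but 9.12 deals only with selection bias and information bias.

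**The concern.** A factor that affects both which class a patient is started on and how soon that patient stops confounds a comparison of persistence between classes. The protocol points to factors of this kind and collects them at index date 1, and SAP 7.3 tests whether baseline characteristics differ by medication. The persistence analysis then makes no use of them.

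The log-rank test asks whether the crude curves are equal. A small p-value between classes may reflect the drugs, the patients chosen for them, or both. The plan attaches no caveat to that p-value, so a report could present patient mix as a difference in persistence between classes. This concerns patient-level mix and would remain within a single country.

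**Working it through.** **Plan's own figure.** There is none to reproduce. Protocol 9.5 gives no formal sample size calculation, and neither document gives a discontinuation rate, an effect size or a significance level for this comparison.

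**Inputs from the documents.** Aspired class sizes are at least 500 for GLP1a and at least 1000 each for SGLT2i and DPP4i (protocol 9.5). Follow-up is one year, plus or minus 2 months (protocol 9.1). The cited Swedish CVD prevalence of 34% (protocol 8.1) serves only as a centre for an illustrative factor.

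**Assumptions not in the documents.** Two-sided 5% level; true class hazard ratio of 1; one binary baseline factor with a prevalence difference between two classes of 0, 10 or 20 points; the factor multiplies the stopping hazard by k = 1.5 or 2; one-year stopping of 10%, 20% or 30% among patients without the factor.

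**Step 1: apparent hazard ratio.** Approximately HR = (1 + (k-1)pA) / (1 + (k-1)pB).

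- 39% v 29%, k = 1.5: 1.195/1.145 = 1.044
- 39% v 29%, k = 2: 1.39/1.29 = 1.078
- 44% v 24%, k = 1.5: 1.22/1.12 = 1.089
- 44% v 24%, k = 2: 1.44/1.24 = 1.161

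**Step 2: rejection by the unadjusted log-rank test.** Exponential times, censoring uniform over 10-14 months, 1000 simulated studies per cell. The three percentages in each cell are for 10%, 20% and 30% stopping.

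| Prevalence, k | 1000 v 1000 | 500 v 1000 |
|---|---|---|
| 34% v 34%, 1.5 | 4.5, 6.0, 4.8 | 5.8, 4.6, 4.5 |
| 39% v 29%, 1.5 | 7.3, 8.5, 7.8 | 5.6, 6.4, 8.0 |
| 39% v 29%, 2 | 11.0, 13.5, 13.8 | 7.4, 10.3, 14.6 |
| 44% v 24%, 1.5 | 11.2, 15.1, 17.6 | 8.5, 13.2, 15.8 |
| 44% v 24%, 2 | 24.1, 37.4, 52.1 | 17.2, 29.2, 37.7 |

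A further set (25% v 50%, k = 2, 20% stopping overall, 2000 simulated studies) has an apparent hazard ratio of 1.50/1.25 = 1.20. It gives 44% rejection at 1000 v 1000 and 29% at 500 v 1000.

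**Step 3: check by formula.** Take 1000 v 1000, 44% v 24%, k = 2, 30% stopping. Expected events are 2000 × (1 - 0.34 × 0.7² - 0.66 × 0.7) = 743. Schoenfeld: √(743 × 0.25) × ln 1.161 ≈ 2.04, and Φ(2.04 - 1.96) ≈ 0.53. The simulation gave 0.521.

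**Step 4: with adjustment.** Stratifying the log-rank test on the factor gives 3.8-6.5% rejection across all cells of the table, which is consistent with 5% given simulation error.

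**The case against.** The strongest reply is that the analysis is descriptive. Objective 5 says assess, whereas objectives 1 and 3 (protocol 8.2) say describe and compare. The SAP calls the analyses descriptive and purely exploratory, and the checklist marks hypotheses and measures of association as not applicable. For crude persistence among patients actually started on each drug, Kaplan-Meier with a log-rank test is a valid method, and a crude difference due to case mix is a real crude difference. The lack of adjustment is also disclosed, since item 10.5 is ticked No.

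Much of this stands. It limits the point to interpretation but does not remove it. SAP 7.4 adds a between-subgroup p-value that objective 5 did not ask for. The exploratory label is used to waive multiplicity correction and does nothing to separate class from patient mix.

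Four stronger readings are tempting and are not supported:

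- *The study presumes that starters of every class differ in age, kidney function, HbA1c and so on.* The abstract says only that "patient characteristics might differ between patients initiating empagliflozin or other glucose lowering drugs". No passage states an expected difference in those items, and protocol 8.1 says that such information is lacking in the region.
- *The 30-50% figures are error rates of the planned test.* They apply only to the question of a class difference at equal patient mix, which the plan never poses.
- *No adjusted analysis exists anywhere.* SAP 7.5 has a contents entry without visible text, so only the visible text can be judged.
- *Section 9.9 names every listed factor as a confounder.* Its clause on influence may attach only to the socioeconomic factors. That narrower reading is still enough for the point.

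**Conclusion.** The point holds as one of interpretation on a secondary outcome. In the visible text the only comparison of time to discontinuation between classes is unadjusted, no covariates are named, and section 9.12 does not support the checklist's Yes on measuring confounding. The crude p-value cannot carry a statement about class differences in persistence.

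The size is unknown from the documents. Under the assumptions above, one weak factor (10-point imbalance, hazard ratio 1.5) barely matters, at about 6-9% rejection. One strong factor (20-25 points, hazard ratio 2) gives roughly 30-50% when 20-30% stop. The class sizes used are recruitment aspirations at index date 1. The index date 2 set may be smaller because of the extra consent and loss to follow-up (protocol 9.12), which would lower the rejection rates but not the bias in the hazard ratio.

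**What to change.** In SAP 7.4:

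1. First define the event and the censoring rule. Protocol 9.3.2 lists death and loss to follow-up as reasons for discontinuation, and stop dates are recorded only if available.
2. Keep Kaplan-Meier and log-rank, labelled as crude and descriptive.
3. Add a supportive Cox model by drug class on the FAS. SAP 6.3 and 7 assign index date 2 outcomes to the FAS while SAP 7.4 names the PPS, so settle this in the same edit.
4. Adjust for data collected at index date 1: age, sex, time since diagnosis, BMI, established CVD, concomitant insulin or sulfonylurea, type of health insurance and physician specialty. Stratify by country, since section 9.9 names availability and reimbursement. Add HbA1c and eGFR in a second model.
5. Report the adjusted hazard ratio with its 95% CI beside the crude result, and make no statement about class differences in persistence from the crude p-value alone.

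The cost is SAP wording and two models, with no new data. Patients with a missing covariate drop out of the adjusted model under SAP 6.6, which is why the laboratory values go in a second model. Adjustment removes only confounding by the measured factors. Changing protocol 9.3.3 as well would need an amendment, so the change can be made in the SAP.
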